8.7 Reporting of Unanticipated Problems

There are types of incidents, experiences and outcomes that occur during the conduct of human subjects research that represent unanticipated problems but are not considered adverse events. For example, some unanticipated problems involve social or economic harm instead of the physical or psychological harm associated with adverse events. In other cases, unanticipated problems place subjects or others at increased risk of harm, but no harm occurs.

Upon becoming aware of any incident, experience, or outcome (not related to an adverse event) that may represent an unanticipated problem, the investigator should assess whether the incident, experience, or outcome represents an unanticipated problem. The incident, experience or outcomes is considered unanticipated if it meets all of the following criteria:

1. Unexpected (in terms of nature, severity, or frequency);

2. Related or possibly related to participation in the research; and
3. Suggests that the research places subjects or others at a greater risk of harm than was previously known or recognized.

If the investigator determines that the incident, experience, or outcome represents an unanticipated problem, the investigator must report it to the local IRB as per local guidelines.

8.8 Unblinding Procedures

Not applicable

8.9 Stopping Rules

See section 11.1 **Safety Monitoring and Stopping Rule**. The DSMC will have oversight on the safety and data integrity of the study on an ongoing basis.

9.0 DRUG INFORMATION

9.1 IONIS-AR-2.5_{Rx} (or specifically ISIS 560131; formerly known as AZD5312)

IONIS-AR-2.5_{Rx} is an ASO targeting a region of the AR that results in selective and specific inhibition of full length, mutated, and splice-variant AR proteins.

IONIS-AR-2.5_{Rx} was designed with the purpose of specifically suppressing human AR expression, thereby providing potential therapeutic benefit to the patients who became unresponsive to traditional anti-hormonal therapies. Preclinical studies indicate that IONIS-AR-2.5_{Rx} suppresses several other AR-regulated genes, suggesting a potential for this agent to be used as a cancer therapy where aberrant AR-signaling drives the disease progression.

Nomenclature

Laboratory Code: IONIS-AR-2.5_{Rx} pentadecasodium

General properties

IONIS-AR-2.5_{Rx} is an amorphous powder and a pentadecasodium salt. IONIS-AR-2.5_{Rx} pentadecasodium is freely soluble in water and has solubility >250 mg/mL at 25°C.

Presentation

The drug product is presented as a sterile solution for injection/infusion filled into 2 mL clear glass vials. Each vial contains an extractable volume of at least 1.2 mL of a 167 mg/mL solution of IONIS-AR-2.5_{Rx} (as the free acid) giving a maximum dose per vial of 200 mg. The product can be administered by direct injection, or by dilution into 0.9% sodium chloride for infusion. The formulation should be prepared and administered according to the handling instructions provided. The vials are intended for single use only.

Composition

The composition of IONIS-AR-2.5_{Rx} solution for injection/infusion is IONIS-AR-2.5_{Rx}, water for injection (Ph Eur or USP), pH adjusted as needed with either sodium hydroxide or hydrochloric acid to pH 8.

Storage conditions

The product should be stored in the pack provided and used as detailed in the handling instructions. Store refrigerated at 2-8°C protected from light.

Intravenous Dose Preparation

1. Obtain required materials:

- 250 mL Normal Saline I.V. Bag
- Study Drug Vials

- Filter Needles 19G or 18G, 5 micron (Becton Dickinson Part # 305200 or 305201 or equivalent)
- Regular 18-22 Gauge Needles

2. Volume of drug to yield the intended dose of 900 mg for AR
3. Warm vial(s) to room temperature for approximately 15 minutes and record the patient number on each vial before dose preparation.
4. Use a filter needle 19G or 18G, 5 micron (Becton Dickinson Part # 305200 or 305201 or equivalent) to withdraw study drug from vials.
5. Remove the used filter needle, replacing it with a regular 18-22-gauge needle.
6. Transfer the study drug to the 250 mL Normal Saline I.V. bag. Vials are for single-use only.
7. Label the I.V. bag per your institution's procedures. Include a label with the statement "Caution: New Drug – Limited by Federal (or United States) law to investigational use". Record on the label the total volume contained in the I.V. bag. Be sure to include in the total volume, the overfill (assume 25 mL unless otherwise known) and the volume of study drug that was added.
8. Start infusion within 2 hours of preparation if kept at room temperature or within 24 hours if refrigerated at 2-8°C.

Availability

- Provided by Ionis Pharmaceutical
- Under no circumstance will the study medication IONIS-AR-2.5_{RX} be used other than as directed by the protocol.

Drug Accountability

The investigator, or a responsible party designated by the investigator, must maintain a careful record of the inventory and disposition of the investigational drug IONIS-AR-2.5_{RX}. The drug accountability records will capture drug receipt, drug dispensing, drug return and final disposition.

Clinical Experience with IONIS-AR-2.5_{RX}:

The first-time-in-patients (FTIP) study, D5860C00001: A Phase I, open-label, multicenter dose-escalation study to investigate the safety and pharmacokinetics of IONIS-AR-2.5_{RX} in patients with advanced solid tumors where the androgen receptor pathway is a potential factor was conducted. Patients are administered IONIS-AR-2.5_{RX} IV on Days 1, 4, 8, 11, 15, and 22 of Cycle 1 and Days 1, 8, 15, and 22 of each subsequent 28-day cycle in an accelerated 3+3 dose escalation. Preliminary PK and safety data are presented in the following sections.

Pharmacokinetics and drug metabolism in humans

Study D5860C00001: The pharmacokinetics of the dose levels of 150, 300, 600, and 900 mg were assessed in 4 cohorts. Intravenous infusion doses of IONIS-AR-2.5_{RX} were administered over 1 hour in Cycle 1 on Days 1, 4, 8, and 11 (± 2 days). Blood samples were obtained over a 24-hour period on Day 1 and prior to dosing on Days 4, 8, and 11. Patients also received weekly treatments on Days 15 and 22 to complete Cycle 1. During subsequent cycles, patients received once weekly treatments on Days 1, 8, 15, and 22 (± 2 days). In Cycle 2, blood samples were obtained over a 24-hour period on Day 22 to characterize the PK profile on that day.

Additional samples were taken prior to the first dose during Cycles 3 and 4, during which doses were administered on Days 1, 8, 15, and 22 (± 2 days).

Cohort 1 (150 mg)

During Cohort 1, PK data was collected for 3 patients on Cycle 1 Day 1 and for 2 patients on Cycle 2 Day 22. The Cycle 1 Day 1 Cmax values averaged 32.4 $\mu\text{g}/\text{mL}$, Tmax occurred at the end of the infusion sampling time (1 hour).

The results of the Cycle 2 Day 22 PK parameter analysis were very similar to Cycle 1 Day 1 results; Cmax values averaged 26.1 $\mu\text{g}/\text{mL}$, Tmax occurred at the end-of-infusion sampling time (1 hour).

Cohort 2 (300 mg)

During Cohort 2, one of the 3 patients had blood samples taken after the end of infusion rather than at the beginning, both on Cycle 1 Day 1 and on Cycle 2 Day 22, so the peak concentrations were not determined for that patient, but rather for the 2 other patients in the cohort. The Cycle 1 Day 1 Cmax values averaged 49.0 $\mu\text{g}/\text{mL}$, Tmax occurred at the end-of-infusion sampling time (1 hour).

For Cycle 2 Day 22, Cmax values averaged 42.5 $\mu\text{g}/\text{mL}$, Tmax occurred at the end-of-infusion sampling time (1 hour).

Cohort 3 (600 mg)

During Cohort 3, one of the 3 patients had blood samples taken after the end of infusion rather than at the beginning, both on Cycle 1 Day 1 and on Cycle 2 Day 22, so the peak concentrations were not determined for that patient, but rather for the 2 other patients in the cohort. The Cycle 1 Day 1 Cmax values averaged 61.3 $\mu\text{g}/\text{mL}$, Tmax occurred at the end-of-infusion sampling time (1 hour).

For Cycle 2 Day 22, Cmax values averaged 58.3 $\mu\text{g}/\text{mL}$, Tmax occurred at the end-of-infusion sampling time (1 hour).

Cohort 4 (900 mg)

During Cohort 4, PK data was collected for 5 patients on Cycle 1 Day 1 and for 2 patients on Cycle 2 Day 22. The Cycle 1, Day 1 Cmax values averaged 102 $\mu\text{g}/\text{mL}$, Tmax occurred at the end-of-infusion sampling time (1 hour).

For Cycle 2 Day 22, Cmax values averaged 72.5 $\mu\text{g}/\text{mL}$, Tmax occurred at the end-of-infusion sampling time (1 hour).

Urinary excretion

Twenty-four-hour urinary collections were made in 2 intervals (0 to 8 and 8 to 24 hours) on Cycle 1 Day 1 and Cycle 2 Day 22. The results of the analysis showed:

- Cohort 1 (150 mg) - the amount of unchanged drug excreted in the urine ranged from 1.04 to 9.96 mg, accounting for 0.694% to 6.94% of the administered dose.

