5.0 TREATMENT PLAN

5.1 Treatment Dosage and Administration

Protocol treatment must start within 14 business days of enrollment to the study.

5.1.1 Overall Treatment Plan:

Phase Ib/II: All registered subjects will be treated with IONIS-AR-2.5_{Rx} (ASO) in combination with enzalutamide. IONIS-AR-2.5_{Rx} will be given intravenously in 60-minute infusions on Days 1, 4, 8, 11, 15 on cycle 1, then on days 1, 8, 15 in subsequent 21-day cycles. Enzalutamide will be taken daily in 21 day cycles starting Day 1 of cycle 1. Treatment will continue until clinical or radiologic progression or unacceptable toxicity. The infusion duration may be extended to 120 minutes for individuals experiencing infusion reactions.

- Baseline archival CRPC tumor tissue will be collected (mandatory) as well as tumor biopsies (optional) after 2 cycles of IONIS-AR-2.5_{Rx} and, tumor biopsies (optional) at progression.

Phase	Agent	Premedications; Precautions	Starting Dose	Route	Schedule
Phase Ib and II	IONIS-AR-2.5 _{Rx}	Per institutional standards for low emetogenic risk	Assigned Dose Level (See table in 5.1.2)	IV infusion over 60 minutes (+/-15 minutes)	*Days 1, 4, 8, 11 and 15 of cycle #1. *Days 1, 8, 15 of each subsequent 21-day cycle
Phase Ib and II	Enzalutamide	No premedications mandated but may be used at investigator discretion/institutional standards	160 mg Qday	Oral	Day 1-21 of each 21-day cycle

Starting on Cycle 1 Day 1, all subjects should take ASA 81 mg PO Qday unless contraindicated.

As noted in section 1.2, the primary study drug IONIS-AR-2.5_{Rx} has been associated with an increased risk of venous thromboembolism (VTE) in early clinical data. Prostate cancer is not associated with a high baseline incidence of VTE, and therefore routine VTE prophylaxis is not required in this patient population based on current NCCN guidelines for cancer-associated VTE. Low-dose aspirin for VTE prophylaxis has been recommended in multiple myeloma patients based on these NCCN guidelines (https://www.nccn.org/professionals/physician_gls/f_guidelines.asp). The overall likelihood of increased risk of VTE events with use of IONIS-AR-2.5_{Rx} in prostate cancer patients is unknown, but given the relatively increased rate of VTE events in the initial study population, VTE prophylaxis appears to be warranted in further clinical study populations.

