Patients in the current phase II trial will receive low dose aspirin (81 mg) daily while receiving study drug to mitigate the apparent increased risk of VTE.

Clotting and bleeding functions including platelet counts will be closely monitored on this study including weekly CBCPD, PT/PTT/INR and reviewed continuously as well at the interim analysis time points. If so needed and indicated by the data, including at interim safety analysis and continually by the Data and Safety Monitoring Board, we would modify the above strategy towards either escalating the prophylactic anti-coagulation to enoxaparin 40 mg daily, for example, or removing the 81 mg daily dose of aspirin.

5.1.2 Upon enrollment, each patient will be assigned a dose level from the statistician to initiate treatment. (See Section 11 for further details.)

Assigned Dose level (TITE-CRM):

Assigned Dose Level	Enzalutamide Dose	IONIS-AR-2.5 _{Rx} Dose
3	160 mg	900 mg
2	160 mg	750 mg
1	160 mg	600 mg

5.1.3 Definition of Dose Limiting Toxicity (DLT):

Excessive toxicity/dose limiting toxicity (DLT) will be defined as any Grade 3 or higher toxicity (as defined by CTCAE v5.0) that occurs during the DLT evaluation period (2 cycles plus labs prior to start of cycle 3). Toxicity that is clearly and directly related to the primary disease or to another etiology is excluded from this definition. The following will be DLTs:

- Liver transaminase elevation Grade 2 lasting 14 calendar days or more OR Liver transaminase elevation Grade 3 or 4
- Grade 3 or Grade 4 febrile neutropenia will be a DLT regardless of duration or reversibility
- Grade 3 thrombocytopenia that IS associated with clinically significant bleeding that requires medical intervention

The DLT Definition excludes the following conditions:

- Grade 3 fatigue lasting ≤ 7 days
- Grade 3 endocrine disorder (thyroid, pituitary, and/or adrenal insufficiency) that is managed with or without systemic corticosteroid therapy and/or hormone replacement therapy and the subject is asymptomatic
- Grade 3 infusion-related reaction (first occurrence and in the absence of steroid prophylaxis) that resolves within 6 hours with appropriate clinical management
- Grade 3 or 4 lymphopenia
- Grade 3 or 4 neutropenia that is not associated with fever or systemic infection that improves within 7 days
- Grade 3 thrombocytopenia that is not associated with clinically significant bleeding that requires medical intervention, and improves by at least 1 grade within 3 days

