5.2.1 IONIS-AR-2.5_{Rx}

IONIS-AR-2.5_{Rx} Dose Modification Levels

Dose reduction levels	Assigned Dose Level = 1	Assigned Dose Level = 2	Assigned Dose Level = 3
Starting Dose	600 mg	750 mg	900 mg
-1	450 mg	600 mg	750 mg
-2	300 mg	450 mg	600 mg
-3	150 mg	300 mg	450 mg

Hematological Toxicities

Hematological Toxicity Dose Reductions for IONIS-AR-2.5 _{Rx} (AR ASO)		
ANC ¹	Platelets	Action
≥ 1,500/µL or 1000-1499/µL or 500-999/µL or	≥100,000/µL 75,000-99,000/µL 50,000-74,000/µL	None. -1 st Occurrence: Hold current dose until ANC ≥ 1,500/µL and platelets ≥ 100,000/µL. Do not replace missed doses. Restart IONIS-AR-2.5 _{Rx} at the next lower dose level as available. -2 nd Occurrence: Hold current dose until ANC ≥ 1,500/µL and platelets ≥ 100,000/µL. Do not replace missed doses. Restart IONIS-AR-2.5 _{Rx} at the next lower dose level as available. -3 rd Occurrence: Hold current dose until ANC ≥ 1,500/µL and platelets ≥ 100,000/µL. Do not replace missed doses. Restart IONIS-AR-2.5 _{Rx} at the next lower dose level as available. -4 th Occurrence: Discontinue protocol therapy. -1 st Occurrence: Hold current dose until ANC ≥ 1,500/µL and platelets ≥ 100,000/µL. Do not replace missed doses. Restart IONIS-AR-2.5 _{Rx} at the next lower dose level as available. -2 nd Occurrence: Hold current dose until ANC ≥ 1,500/µL and platelets ≥ 100,000/µL. Do not replace missed doses. Restart IONIS-AR-2.5 _{Rx} at the next lower dose level as available. -3 rd Occurrence: Hold current dose until ANC ≥ 1,500/µL and platelets ≥ 100,000/µL. Do not replace missed doses. Restart IONIS-AR-2.5 _{Rx} at the next lower dose level as available. -4 th Occurrence: Discontinue protocol therapy.

<500/ μ L or	<50,000/ μ L	
-1st Occurrence: Hold current dose until ANC \geq 1,500/μL and platelets \geq 100,000/μL. Restart IONIS-AR-2.5_{Rx} at the next lower dose level as available.
 
-2nd Occurrence: Hold current dose until ANC \geq 1,500/μL and platelets \geq 100,000/μL. Do not replace missed doses. Restart IONIS-AR-2.5_{Rx} at the next lower dose level as available.
 
-3rd Occurrence: Discontinue protocol therapy.

¹Note: G-CSF (Filgrastim) may be added for low ANC on day of treatment BEFORE a dose reduction is instituted at treating physician's discretions. Neulasta® is NOT allowed.
		

Dose Modifications for Hepatic Toxicity

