11.1 Study Design

Dose Assignment in Phase 1b: The first patient will be enrolled to dose level 3 of IONIS-AR-2.5_{Rx}, in combination with a fixed dose of enzalutamide. Subsequent dose assignments to dose levels 1, 2 or 3 will be based upon the statistical-model-based TITE-CRM design. This trial will seek to estimate the MTD, the true value of which is defined as the dose level with probability of DLT closest to but not exceeding 35%.

Final Efficacy Analysis After all 35 evaluable patients are enrolled and the PSA response endpoint is recorded for all patients, we will fit the Bayesian isotonic regression model on all patients' data. If the probability that the PSA response rate at the final estimated dose exceeds 5% is at least 0.95, the trial will have successfully completed its primary objective.

Interim Analysis/Criteria for Stopping Study Continuous monitoring of safety is built into the TITE-CRM model, and the trial will stop at any point in which all dose levels have a model-estimated probability of DLT exceeding 37.5%.

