11.6 Data Analysis Plans

11.6.1 Primary Objective Analyses

Dose Assignment with toxicity assessment The first patient will be assigned to dose level 3. For each patient after the first, we will estimate the one-parameter power model, $\Pr(\text{Tox}|\text{dose } j) = (d_j)^{\exp\{b\}}$, where $\{d_1, d_2, d_3\} = \{0.10, 0.20, 0.30\}$ is the pre-specified skeleton (the anticipated probabilities of DLT at each dose level) and the parameter b is to be estimated, using its posterior mean from a Bayesian analysis. We will place a Normal (0, 0.6²) prior on b . Each patient will be assigned to dose level j , $j=1,2,3$, such that the model estimated probability of DLT at that dose level, $(d_j)^{\exp\{b\}}$, is closest to 0.35 but not exceeding 0.375. Any patients who are free of DLT but have only finished t days of their first cycle, $t < 42$, will have their likelihood contribution down-weighted by a factor $(t^2/42^2)$. At any point after the first 6 patients, if the model-estimated rate of DLT at dose level 1 exceeds 0.375, the trial will stop for toxicity.

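### Step 2 of the IV preparation in section 9.1 names a single dose of 900 mg, which fits only an unreduced level 3 patient and conflicts with the patient-specific doses in section 5

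*Combined protocol and SAP*

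**What the plan says.** Section 9.1, under Intravenous Dose Preparation, lists eight steps. Step 2 reads "Volume of drug to yield the intended dose of 900 mg for AR". It states no volume, and none of the eight steps mentions an assigned or reduced dose.

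Elsewhere the dose depends on the patient:

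- The treatment table in section 5.1.1 gives the starting dose of IONIS-AR-2.5Rx as "Assigned Dose Level (See table in 5.1.2").
- Section 5.1.2 says that "each patient will be assigned a dose level from the statistician to initiate treatment" and lists 900 mg (level 3), 750 mg (level 2) and 600 mg (level 1).
- Section 5.2.1 gives three reductions below each starting dose. Its hematological rules, for example, restart the drug "at the next lower dose level as available".
- Section 11.1 puts the first patient on level 3, and then "Subsequent dose assignments to dose levels 1, 2 or 3 will be based upon the statistical-model-based TITE-CRM design".

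Two other statements in section 9.1 bear on the point. Under Availability, the drug may not "be used other than as directed by the protocol". Under Presentation, "The formulation should be prepared and administered according to the handling instructions provided". Those handling instructions are not part of the documents.

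**The concern.** The preparation steps tell the person filling the bag what to draw up. In a trial with three starting doses and reductions below each, a single fixed dose at that point contradicts the dosing section for every patient who is not on unreduced level 3. The mismatch always runs towards too much drug, because 900 mg is the highest dose in the protocol. It is largest for patients whose dose has been cut furthest for toxicity.

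The stake is patient safety at the point of preparation. The rule that the drug be used only as the protocol directs does not remove the conflict, because the protocol itself gives two figures.

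**Working it through.** No sample size, power or error rate is involved. The check compares step 2 with every dose the protocol allows.

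**Inputs**

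- Dose in step 2: 900 mg (section 9.1).
- Starting and reduced doses: the table in section 5.2.1, whose starting row agrees with section 5.1.2.
- Solution strength: 167 mg/mL, with at least 1.2 mL extractable and a 200 mg maximum per vial (section 9.1). Reproducing the stated content: 1.2 × 167 = 200.4 mg, which agrees.
- Overdose (section 9.1): any administered dose above the one the protocol sets for that patient.

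**Step 1. Which cells are 900 mg?** There are 3 levels × 4 rows = 12 cells.

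| Row | Level 3 (mg) | Level 2 (mg) | Level 1 (mg) |
|---|---|---|---|
| Start | **900** | 750 | 600 |
| -1 | 750 | 600 | 450 |
| -2 | 600 | 450 | 300 |
| -3 | 450 | 300 | 150 |

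One cell is 900 mg. The other 12 − 1 = 11 run from 150 to 750 mg.

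**Step 2. Size of the discrepancy if 900 mg were prepared and given.** Ratio = 900 / prescribed dose; excess = 900 − prescribed dose; correct volume = prescribed dose / 167.

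| Prescribed | Cells | Ratio | Excess | Correct volume |
|---|---|---|---|---|
| 900 mg | 1 | 1.0 | 0 mg | 5.39 mL |
| 750 mg | 2 | 1.2 | 150 mg | 4.49 mL |
| 600 mg | 3 | 1.5 | 300 mg | 3.59 mL |
| 450 mg | 3 | 2.0 | 450 mg | 2.69 mL |
| 300 mg | 2 | 3.0 | 600 mg | 1.80 mL |
| 150 mg | 1 | 6.0 | 750 mg | 0.90 mL |

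In each of the 11 cells the ratio exceeds 1, so the dose given would be an overdose as section 9.1 defines it.

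**Step 3. Are the lower doses a real part of the plan?** Section 11.6.1 uses the model Pr(DLT at level j) = d_j^exp(b), with skeleton 0.10, 0.20, 0.30, prior b ~ N(0, 0.6²) and the posterior mean of b. It assigns the level whose estimate "is closest to 0.35 but not exceeding 0.375". Suppose the first patient, at level 3, has a DLT and nothing else is known. The posterior mean of b is −0.349, so exp(b) = 0.7055, and the estimates are:

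- level 1: 0.10^0.7055 = 0.197
- level 2: 0.20^0.7055 = 0.321
- level 3: 0.30^0.7055 = 0.428

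Level 3 is above 0.375, and level 2 is the closest to 0.35 among the rest. The next patient therefore starts at 750 mg. One event is enough to produce a patient for whom step 2 is wrong from the first infusion.

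Appendix E also records that two patients treated at level 3 had toxicity that the study team judged to call for dose modification. The need for doses below 900 mg has thus already come up.

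**The case against.** The case on the other side is strong on likelihood.

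- Section 5 settles the dose. Sections 5.1.1, 5.1.2, 5.2.1, 11.1 and 11.6.1 all agree that it is patient-specific, and nobody reading the whole protocol would conclude that everyone receives 900 mg.
- Section 9.1 recognises this too, since its overdose definition is tied to the dose set for the individual patient.
- Step 2 is a sentence fragment with no verb and no volume. Whoever prepares the bag must work out a volume, presumably from an ordered dose, and separate handling instructions may give the right procedure.
- The synopsis gives 900 mg as the Phase Ib starting dose, so step 2 may simply be a leftover figure.
- Literal use could not exceed 900 mg, which is level 3 of this trial and the single-agent MTD reported in section 1.3 (DLT in 1 of 13 patients at that dose).

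All of this stands, and it keeps the severity low. None of it corrects the figure. The fragment still names one dose, it sits among steps meant to be carried out, and nothing in those steps points to section 5. Handling instructions that are not in the documents cannot be assumed to carry the right dose. That 900 mg lies within the studied range is little comfort for a patient already reduced because of toxicity.

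**Conclusion.** The inconsistency is real and is in the current text. Step 2 is right for 1 of the 12 dose cells and wrong for 11. The size, 1.2 to 6 times the prescribed dose with a ceiling of 900 mg, rests on two conditions: that the step is followed literally, and that the bag is then given. Because section 5 governs, both together are unlikely. This is a low-severity correction.

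A reader might infer more in three ways, and the documents do not support any of them.

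- That the protocol intends a fixed 900 mg for all patients. Section 5 and section 11 plainly say otherwise.
- That overdosing is likely or has happened. Nothing in the documents shows a preparation error, and the dosing section, the overdose definition and possibly the handling instructions all work against one.
- That the dose-finding results or the design are compromised. The assignment model, stopping rule, sample size, endpoints and efficacy analysis do not use step 2. Simulating how many patients would start below level 3 would not change this: it would describe dose allocation, not how often a bag is prepared wrongly.

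**What to change.** In step 2 of section 9.1, replace 900 mg with wording such as: the patient's current assigned or reduced dose (Sections 5.1.2 and 5.2.1). Check that any separate handling instructions say the same.

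Optionally, add the volumes at 167 mg/mL from the second table above, or leave them to the pharmacy or the handling instructions.

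The cost is one phrase and one cross-check. Design, sample size, endpoints and analysis are unchanged.
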